A3. Management of Dysglycemia in Patients on Hemodialysis. Most anti-diabetic drugs require dose adjustments or are contraindicated in patients with advanced CKD or ESRD^{3,4,7}. Thus, ~60-70% of patients with type 2 DM on hemodialysis are managed with insulin therapy¹⁸⁻²⁰, or with a combination of insulin and oral agents (sulfonylureas) which are associated with increased risk of adverse events²⁰. In our institution, 56% of patients with type 2 DM are currently treated with insulin therapy, 37% received no therapy, and 7% are treated with oral agents: 40% secretagogues and 60% incretins. Notably, treatment with insulin and/or sulfonylureas is associated with a higher risk for emergency department (ED) visits and hospitalization for hypoglycemia among patients with ESRD²⁰. In addition, hypoglycemia is associated with increased risk of cardiac arrhythmias²¹, strokes²², seizures²³, and sudden cardiac death^{23,24}. Nevertheless, the evidence on the association between hypoglycemia and different anti-diabetic agents is limited^{20,25}. In a small study (n: 10) of patients with type 2 diabetes and ESRD, Sobngwi et al. analyzed insulin needs during a euglycemic clamp and using short-term retrospective CGM¹⁶. The authors demonstrated that basal insulin doses decreased by 25% post-hemodialysis, compared to the pre-dialysis day. In a similar study using CGM, but in patients with no diabetes and ESRD, the same group reported a tendency towards lower glucose during the hemodialysis sessions, with a nadir at the 3rd hour²⁶. However, no prospective intervention study has been performed using CGM to adjust insulin therapy in ESRD patients. We hypothesize that the high risk of hypoglycemia in this population relates to the high insulin and sulfonylurea utilization and to poor treatment dose adjustments due to lack of reliable glucose monitoring data to guide therapy.

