Basal Insulin Dose Adjustments	Adjust dose of basal insulin based on the prior 24-hours glucose values. If hypoglycemia <70 mg/dL (at least once), reduce daily dose by 30% the day prior to dialysis, or by 20% during the dialysis day ¹⁶ .
Pre-Prandial Bolus Insulin Dose Adjustment	After 3 days, If pre-meal glucose > 180 mg/dL: 1) increase insulin by 2 units before each meal. If glucose > 280 mg/dL in 3 consecutive days, increase insulin by 4 units and call study team.

Device Information: Dexcom G6 CGM

The proposed CGM to be used in this study is the Dexcom G6, a factory-calibrated CGM system⁴³, that is innovative in many aspects: 1) it does not require finger stick POC BG for calibration, 2) the sensor is smaller, compact, light-weight, 3) has no interference with several substance and drugs, and 4) protective “urgent low soon” alarm, with proven prediction of hypoglycemia within 20 minutes in advance^{39,44}. The sensor uses a novel semi-permeable membrane that blocks interference with most clinically relevant substances, including high levels of urea and creatinine, and commonly used medications^{45,46}. Dexcom G6 CGM is a commercially-available, minimally invasive sensor, with a flexible and thin wire that is inserted into the abdominal subcutaneous tissue. In addition, subjects will check their POC BG (standard of care) using commercially available glucose meters, approved to be used in dialysis populations. Medical history and demographics will be collected from the medical record.

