5.6.2 DOSING AND ADMINISTRATION

See above Table for Aim 2

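### The basal insulin table's larger percentage cut falls on the day before dialysis, in unexplained tension with the protocol's own summary of the study it cites, and its day wording has two readings

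*Combined protocol and SAP*

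**What the plan says.** The guidelines table in section 5.6.1 has a row on basal insulin. It opens with "Adjust dose of basal insulin based on the prior 24-hours glucose values". If there has been at least one value below 70 mg/dL, the participant is told to "reduce daily dose by 30% the day prior to dialysis, or by 20% during the dialysis day". The rule ends with a superscript to reference 16.

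Section 2.2 (A3) describes reference 16 as a study of 10 people with type 2 diabetes and ESRD that "analyzed insulin needs during a euglycemic clamp and using short-term retrospective CGM¹⁶". It reports the result in one sentence: "The authors demonstrated that basal insulin doses decreased by 25% post-hemodialysis, compared to the pre-dialysis day". The next sentence describes work by the same group in people on dialysis without diabetes (reference 26), which "reported a tendency towards lower glucose during the hemodialysis sessions, with a nadir at the 3rd hour".

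Section 5.6.2, on dosing and administration, consists only of a pointer: "See above Table for Aim 2". Section 2.3.1 says that everyone in the interventional study receives guidance on adjusting insulin from CGM or POC readings. The heading above the table likewise covers both kinds of monitoring.

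**The concern.** Two sections rely on one reference and appear to point different ways. The background has basal doses higher before dialysis and lower after it. The table takes the larger percentage off on the day before dialysis and the smaller on the dialysis day. A reader who follows the citation back to section 2.2 finds neither percentage and no step from one to the other.

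The row is also ambiguous in use. The day phrase could mark the day of the low glucose or the day on which the smaller dose is taken. The trigger looks back 24 hours, so these can be different calendar days.

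This matters for safety first. The table is written for participants to act on, and it is all that the dosing section points to for Aim 2. It also bears on the primary outcome, percentage of time below 70 mg/dL. An insulin rule that two participants can read differently makes the intervention harder to describe and to reproduce.

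**Working it through.** No sample-size, power or alpha calculation bears on this point, and the plan states no figure of its own to reproduce. The 25% cannot be checked, because the cited study is not part of the documents. The check sets the two texts side by side and works out the dose ratio that each implies.

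**Inputs**
- Cut on the day before dialysis: 30% (section 5.6.1, table).
- Cut on the dialysis day: 20% (same row).
- Trigger: at least one value below 70 mg/dL, judged on the previous 24 hours (same row).
- Reported difference after dialysis against the pre-dialysis day: 25% lower (section 2.2, A3).
- Source cited for both: reference 16.

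**Side by side**

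| | Section 2.2 summary | Section 5.6.1 table |
|---|---|---|
| Kind of statement | Observed difference in basal dose | Correction after a low glucose |
| Time labels | Post-dialysis; pre-dialysis day | Day before dialysis; dialysis day |
| Percentages | 25% | 30% and 20% |
| Rationale linking the two | None | None |

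**Ratio in the summary.** Post-dialysis over pre-dialysis day = 1 − 0.25 = 0.75.

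**Ratio in the table, one equal usual dose.** Assumption: the usual dose is 100 on both days and both cuts are applied.
- Day before dialysis: 100 × (1 − 0.30) = 70.
- Dialysis day: 100 × (1 − 0.20) = 80.
- Ratio: 80/70 = 1.143, so the dialysis-day dose is about 14% higher.

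**Ratio in the table, usual doses already following the summary.** Assumption: usual doses are 100 on the day before and 75 on the dialysis day.
- Day before dialysis: 100 × 0.70 = 70.
- Dialysis day: 75 × 0.80 = 60.
- Ratio: 60/70 = 0.857.

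The ratio therefore runs from 0.86 to 1.14 over these two baselines and crosses 1. The order of the resulting doses depends on a baseline that the documents do not give. The order of the percentage cuts does not: 30% exceeds 20% under either.

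**The two readings of the day label.** Assumption for illustration: a low occurs on the day before dialysis, and the next basal dose is taken on the dialysis day, from a usual dose of 100.
- If the label marks the day of the low, the cut is 30% and the dose is 70.
- If the label marks the day of the reduced dose, the cut is 20% and the dose is 80.

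Same patient, same event: the two readings differ by 80 − 70 = 10, that is, 10% of the usual dose. The row also gives no rule for a day that is neither a dialysis day nor the day before one.

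**The case against.** The strongest reply is that the two texts do not describe the same thing.

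- **Different quantities.** A typical difference in need and a correction after hypoglycemia can have different gradients without contradiction. This stands. What remains is that the protocol cites the first as support for the second with no linking step.
- **Different time labels.** The post-dialysis period and the dialysis day overlap only in part. This stands too, and it is a reason to define the labels.
- **An anticipatory cut.** A dose lowered the day before might be meant to act in the lower-need period that follows. The direction would then agree with section 2.2. This is possible, but no section says so.
- **The 14% figure.** It needs both cuts, taken from one equal usual dose, while the row joins them with *or* and makes each depend on a recent low. This stands, so the figure can be given only with that assumption and with the 0.86 case beside it.
- **No bias shown.** The same table serves both monitoring methods in a crossover, and both percentages are reductions. This stands as far as it goes. A single value below 70 mg/dL triggers the rule, and section 2.2 says POC testing misses asymptomatic and nocturnal lows, so the rule may be triggered more often under real-time CGM. The documents give no way to size that.

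A reader might infer that the table has the two percentages reversed, that it contradicts reference 16, or that it biases the Aim 2 comparison. The documents support none of these. The only evidence about reference 16 is a one-sentence summary, the quantities and labels differ, and no direction of effect on time below 70 mg/dL can be derived.

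**Conclusion.** The point holds as an unexplained tension between two sections that cite one source. On a plain reading, the table's larger percentage cut falls on the day that section 2.2 describes as the higher-dose day. Neither of its percentages comes from that summary, and the documents offer no rationale. Its size in dose terms is not settled: the table's ratio is 1.14 from an equal baseline and 0.86 from a 100:75 baseline, against 0.75 in the summary.

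The ambiguity in the day label is separate and does not depend on the cited study. In the illustration it moves the dose by 10% of the usual dose.

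Nothing here shows which section, if either, is in error. The point is still worth acting on, because this is an insulin instruction for participants and the dosing section refers to nothing else.

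**What to change.** Before the table is given to participants, sponsor clinicians should:

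1. Check sections 2.2 and 5.6.1 against the cited source and reconcile them.
2. Reword the row so that it states whether each day label refers to the day of the low glucose or the day of the reduced dose, and say what the row intends for days that it does not name.
3. Either correct whichever section is found to be in error, or state the rationale for the percentages and stop citing reference 16 as direct support.

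The cost is a clinical check, a short text amendment and a revised handout. The design, sample size and analysis do not change. No dose or clinical rule is proposed here.

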2.3 RISK/BENEFIT ASSESSMENT

2.3.1 KNOWN POTENTIAL RISKS

1.a. Patients who develop hypoglycemia: We anticipate that ~50% of individuals recruited for this study will develop hypoglycemia by POC BG (as available).

During the observation study, blinded CGM data will be collected. Thus, subjects will be instructed to perform POC BG, as standard of care, for glucose monitoring. The study team will provide subjects with training on hypoglycemia management and prevention. If the study subject experiences hypoglycemic symptoms during the dialysis/blood glucose testing, we will notify the dialysis team to check a blood glucose and treat per standard of care. If POC BG or -YSI glucose is < 70 mg/dl, subjects will be given corrective measures, per standard of care, and communicate to their treating physician regarding subject's insulin doses and the need for follow-up for treatment of diabetes.

During the interventional study, all subjects will receive standard guidelines on how to adjust insulin based on CGM or POC BG data, and how to treat hypoglycemia per standard of care. The sensors provide a predictive hypoglycemia alarm ("predictive urgent low soon") that will alarm the subject within the preceding 20 minutes of a glucose < 55 mg/dl. The main objective of our RCT is to prevent hypoglycemia.

1.b. Risk of hyperglycemia.

We will exclude subjects with severe hyperglycemia (BG > 400 mg/dl) during consent/randomization. These subjects will be notified of the findings and advise to communicate with their treating physician for treatment adjustments.

1.c. Phlebotomy: Risks associated with phlebotomy and IV insertion are low and include small amounts of pain, possible bruising, swelling, redness, and rarely an infection at the site. However, we will collect blood from the pre-dialysis circuit and after the dialysis nurse inserted the dialysis needle. Approximately, ~5-10 ml of blood will be obtained during the dialysis for glucose testing (Aim 1b). These risks will be shared with the participants during informed consent and before starting the studies.

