Investigator, would interfere with their participation in the trial (e.g., marked visual or hearing impairment, active alcohol or drug abuse, mental illness) or pose excessive risk to study staff handling venous blood samples. Situations that will limit the subject's ability to comply with the protocol (per investigator discretion), active malignancy, unable to give informed consent, at least 10% of time spent in clinical relevant hypoglycemia (<54 mg/dl) during blinded CGM period, significant hypoglycemia (< 40 mg/dL) or severe hyperglycemia (BG > 400 mg/dL) during randomization, extensive skin abnormalities at insertion sites, pregnancy or breastfeeding, severe anemia (Hemoglobin < 5 mg/dl) or polycythemia (Hemoglobin >17 mg/dl), subjects taking acetaminophen (more than 1 gr every six hours) or hydroxyurea (may cause interference with the sensor membrane).

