Wash-Out Period (week 4-6): After completion of phase 1, all subjects will return to the clinic to remove the CGM and review the POC BG diary. After sensor removal, transmitter will be connected to the computer for data downloading. Sensor will be stored following standard precautions. Study personnel will input required clinical and demographic data into the sensor database software. During this period, no CGM will be worn, and all subjects will be reminded to perform self-monitored BG (SMBG) as usual.

Phase 2 (week 7-10): After completing the wash-out period, subjects initially randomized to the “Usual Care, Phase 1” arm will have a personal/real-time CGM inserted during the visit, and will be trained on how to use CGM to improve glycemic control (as described above) Subjects initially randomized to “Intervention Group, Phase 1” will then cross-over to the “Usual Care Group, and a blinded CGM will be used for up to 4 weeks.

Last Visit (week 10): After completing the 4 weeks’ assignment, subject will come back for CGM removal, if applicable. After sensor removal, transmitter will be connected to the computer for data downloading. Sensor will be stored following standard precautions. Study personnel will input required clinical and demographic data into the sensor database software

Guidelines to improve glycemic control using real-time CGM or POC BG:

Glucose Target	Know your personal glucose targets and take actions to reach them. My pre-meal target is 80 - 180 mg/dl . My post-meal target is < 200 mg/dl (2 hours after the start of a meal).
Low Glucose (Hypoglycemia)	Plan to prevent or to respond to hypoglycemia. Check POC glucose for confirmation. Eat 15 grams of carbohydrates (4 ounces of apple juice, or 4 glucose tablets) and repeat a fingerstick blood glucose measurement 15 minutes later. Repeat treatment if glucose <100 mg/dl every 15 min until BG > 100 mg/dl. Do not inject until glucose > 100 mg/dl.
CGM - Risk of Hypoglycemia (Urgent Low Soon Alarm)	For the “Urgent Low Soon Alarm” (predictive of hypoglycemia <55 mg/dL, within the preceding 20 minutes): 1) Eat 15 grams of carbohydrates and recheck in 15 minutes, 2) avoid injecting insulin or taking anti-diabetic agents until glucose is higher than 100 mg/dL, 3) check POC glucose for confirmation, 4) collect data in the diary.

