8.2 SAMPLE SIZE DETERMINATION

No preliminary data is available on ESRD patients with this device. Heinemann et al.⁴² studied subjects with hypoglycemia treated with insulin. The authors reported medians and interquartile ranges of this outcome under RT-CGM or usual care. Based on these preliminary data, we approximated the standard deviation (SD) of our primary outcome under the normality assumption. This suggests 6.45% as a conservative upper bound for the SD. Assuming 10% attrition rate and 6.45% as the SD of the primary outcome, recruiting 45 subjects would give 90% power to detect a mean difference in percentage time in hypoglycemia range which equals 4.8%, based on a two-sided t-test for a two by two cross-over design, with alpha=0.05.

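### The Aim 2 mealtime-insulin row prints only dose increases, and no line holds the increase after a glucose below 70 mg/dL in the same 3 days

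*Combined protocol and SAP*

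**What the plan says.** Section 5.6.1 gives Aim 2 participants a table for acting on CGM or fingerstick readings. Its row on pre-prandial bolus insulin holds two instructions. The first is "After 3 days, If pre-meal glucose > 180 mg/dL: 1) increase insulin by 2 units before each meal". The second is "If glucose > 280 mg/dL in 3 consecutive days, increase insulin by 4 units and call study team".

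The only dose reduction is in the basal row. After at least one value below 70 mg/dL in the preceding 24 hours, the participant is to "reduce daily dose by 30% the day prior to dialysis, or by 20% during the dialysis day". The low-glucose row adds "Do not inject until glucose > 100 mg/dl", and the row on the predictive low alarm likewise says to wait for a value above 100 mg/dL.

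Section 5.6.2 only points back to this table. Section 2.3.1 says that everyone in the randomized study receives the guidance, whether they use CGM or fingersticks. Section 5.10 leaves treatment to the treating physician. The Schedule of Activities places insulin-adjustment training at V2 and V4.

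**The concern.** Section 2.3.1 states: "The main objective of our RCT is to prevent hypoglycemia". Percentage of time below 70 mg/dL is the Aim 2 primary outcome. Section 2.2 (A3) attributes part of the hypoglycemia risk in this population to poor dose adjustment for want of reliable glucose data. Dose adjustment is therefore one of the routes by which CGM is meant to help, yet the mealtime row makes no use of information about lows.

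A participant who follows the table can raise mealtime insulin within days of a low. For the 2-unit step nobody else need be involved, because the call to the study team is attached only to the step at 280 mg/dL. What is at stake is the safety and quality of treatment in either phase.

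**Working it through.** No figure in the plan needs reproducing. The check is of the text, followed by what the documents' numbers can and cannot show.

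**1. Does any printed line hold the increase?**

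- Mealtime row, 2-unit step: an increase, with no condition about lows and no call.
- Mealtime row, 4-unit step: an increase with a call, and no condition about lows.
- Basal row: a reduction, but of basal insulin only. Its look-back is 24 hours, so a low on the first of three days lies outside it when the mealtime increase falls due.
- Low-glucose and predictive-alarm rows: they delay an injection until glucose is above 100 mg/dL. They do not change a later dose.
- Sections 2.3.1, 5.6.2, 5.10 and 5.10.1: general statements or a cross-reference. None makes a mealtime increase conditional on the absence of a low.

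**2. Does the answer depend on how the trigger is read?** Take the strictest reading, in which every pre-meal value over 3 days must exceed 180 mg/dL. Suppose one overnight value in that window is below 70 mg/dL. It is not a pre-meal value, so the trigger is still met and the increase goes ahead. Looser readings make the increase easier to reach. The hold is missing on all of them.

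**3. How common are lows expected to be?**

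- Section 2.3.1 expects about 50% of recruits to have hypoglycemia on fingerstick readings. With the 45 participants planned for Aim 2: 0.50 × 45 = 22.5, about 22. Section 5.1 admits mealtime-insulin users but gives no share. Assuming 30% to 100%, unrelated to who has lows: 0.30 × 22.5 = 6.75 up to 22.5, about 7 to 22 participants.
- Section 8.2 powers the trial for a difference of 4.8 percentage points. A reduction of that size requires a control-phase mean of at least 4.8%: 0.048 × 1,440 = 69.1 minutes a day, or 3 × 69.1 = 207 minutes (about 3.5 hours) in 3 days.
- Section 5.2 excludes people with "at least 10% of time spent in clinical relevant hypoglycemia (<54 mg/dl) during blinded CGM period". Since 0.10 × 24 = 2.4 hours, someone with just under 2.4 hours a day below 54 mg/dL can be randomized.

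These figures concern lows alone. The event that matters is mealtime insulin, a low and a qualifying pre-meal high within one 3-day window. The documents give no figure for that.

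**4. How large is the step?** Let k be the number of mealtime injections a day (assumed 1, 2 or 3). If every mealtime dose is raised, the first step adds 2k = 2, 4 or 6 units a day. The basal dose at which this equals the basal cut is 2k/0.30 = 6.7, 13.3 or 20 units for the 30% cut, and 2k/0.20 = 10, 20 or 30 units for the 20% cut. Below those doses total units rise; above them they fall. This is a unit count only, because basal and mealtime units are not interchangeable.

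**The case against.** The strongest reply is that the table already leans toward safety. One low cuts basal insulin by 20% to 30% within a day, whereas a mealtime increase waits 3 days. Injections stop until glucose is above 100 mg/dL, the larger step requires a call, participants are trained, and the physician remains in charge. It is guidance to patients, not forced titration. Lowering basal while raising mealtime insulin for persistently high pre-meal values is not self-evidently wrong, and the protocol sets no standard by which any low must veto an increase. All of this stands as mitigation and keeps the point modest. None of it supplies the missing line.

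The row also prints a 1) with no 2), so an item may have dropped out of the table. The sponsor can check the participant handout. If a hold is there, the point closes. Nothing available shows one.

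A reader might infer more than the documents support:

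- **One low episode both cuts basal and raises mealtime insulin through rebound.** This needs the trigger to be a single high value. If 3 days means a sustained pattern, one rebound does not trigger it. Sections 2.2 (A5) and 4.1 offer rebound as a hypothesis.
- **A count of participants harmed, or net harm.** The 7 to 22 counts people with any low under an assumed share. The 4.8 points is a planning difference whose SD was borrowed from another population, and the 10% criterion is a ceiling. Total insulin can fall as well as rise.
- **Every mealtime dose rises when one meal is high.** This disappears if the row is read meal by meal.
- **Bias between phases, or loss of power.** The same table serves both phases, and the sample-size calculation does not use it.

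**Conclusion.** The point holds as a gap in the printed guidance. The mealtime row contains only increases, no line withholds them after a value below 70 mg/dL in the same 3 days, the only reduction is to basal insulin, and the 2-unit step can be taken without a clinician. This rests on the table as printed and on no particular reading of the trigger. The effect on time below 70 mg/dL cannot be derived from the documents. It is an inexpensive patient-safety improvement that the sponsor should make, given the trial's stated objective. It is not a threat to the comparison.

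**What to change.** Add to the mealtime row: *Do not increase mealtime insulin if any reading in those 3 days was below 70 mg/dL; contact your treating physician about the dose.* Apply the same hold to the 280 mg/dL step and keep its existing call to the study team. State that an increase applies to the mealtime dose linked to the high reading.

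The hold should direct participants to the treating physician, not the study team. Section 5.8 keeps investigators from real-time access to the primary outcome data and masked until all phases are complete. Calls about lows would report them to the team and add study contact that differs between phases.

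Because the reason is safety, apply the new row to all participants once the amendment is approved, including those already randomized. Record the date it took effect for each participant, so that those whose two phases fall under different rules can be identified. Teach it at the V2 and V4 training.

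The cost is one reworded row, a revised handout and IRB review, with no extra patients and one date to record per participant. Correction of hyperglycemia after a low will be slightly slower. The hold will be triggered more often in the real-time CGM phase, because CGM shows lows that fingersticks miss (Section 2.2, A2).
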